5.1 Software

All analyses will be done using SAS version 9.3 (SAS Inst. Cary, NC, USA) or Stata version 10.1 or higher (StataCorp, TX, USA). The WHO 2006 Child Growth Standards will be used for age-and-sex standardization of child weight, length, head circumference, arm circumference and weight-for-height.

5.2 Sample size and attrition

Sample sizes by group will be presented for each time point (**Table 1 and Figure 1**), and differential attrition will be assessed with chi-square tests at each time point.

5.3 Background characteristics

Selected background characteristics (measured at baseline) will be examined by group for baseline and endline samples (**Table 2**). Feeding practices at baseline will be presented, by group (**Table 3**).

5.4 Analysis of the effect of the intervention

General comments:

- a. The hypothesis stated in section 3 is a non-equivalence hypothesis. However, the study was not powered for IYCF practices outcomes and we are severely underpowered for equivalence analyses, particularly for dichotomous outcomes (such as prevalence of continued breastfeeding at any time point). Therefore the more traditional approach in the nutrition literature of analyzing for significant differences will be followed in the first instance. This limitation will be clearly explained in the discussion section of any publication.
- b. For quasi-continuous variables, we will supplement this with an equivalence approach to hypothesis testing, to help inform conclusions from this analysis.

Analysis of the effect of the intervention will follow these steps:

- a. A set of pre-specified potential covariates will be examined through reviewing correlations and collinearity (e.g. using "collin" command in Stata). Variables with VIF > 10 will be assessed and a reduced set of variables will be retained, such that all VIF are < 10.
- b. We will test the null hypothesis of no difference among the four treatment groups (iLiNS-DOSE) using ANCOVA or logistic regression, and controlling for the prespecified covariates (most of which are also potential effect modifiers, see below).
- c. For all analyses, if the global null hypothesis is rejected at 0.05 level, then we will perform post-hoc pairwise comparisons of all four groups using appropriate

adjustments for multiple comparisons and Scheffe's test to examine other contrasts of interest.

- d. The effects of potential effect modifiers will be assessed with an interaction term in the ANCOVA or logistic regression model. Each interaction will be assessed separately.
- e. Significant interactions (p < 0.05) will be further examined with stratified analyses, estimation of separate regression lines, or estimation of adjusted means at key points of the covariate, in order to understand the nature of the effect modification.
- f. For quasi-continuous outcomes (number of fruit/vegetable groups consumed yesterday; number of animal-source food groups consumed yesterday, and fruit/vegetable and animal-source food scores for last week) equivalence will be assessed based on defined margins. Margins for yesterday will be ±1.0 (one more or one fewer fruit vegetable group; one more or one fewer animal-source food group). For scores for last week, the margin will be ±5 points for the fruit/vegetable scores and ±4 for animal-source foods (~= a difference of one group/day in each).
- g. We will assess equivalence in the context of ANCOVA models, controlling for the same pre-specified covariates as noted above. Equivalence will be determined to exist if the 90% confidence interval for the difference between the means is entirely contained within the negative and the positive values of the equivalence margin.
- h. Confidence intervals will be adjusted for multiple comparisons.
- i. For each outcome, if results are inconclusive, all LNS groups will be combined and 2-group comparisons will be made, to improve power to detect differences.

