The iLiNS-DOSE trial was designed to study the impact of a 12-month LNS provision to infants and young children on their growth, nutritional status and a number of other health outcomes. For this purpose, a total of 1932 infants were enrolled in rural Malawi, randomized to receive for 12 months either no supplement or one of five alternative LNS-preparations (six study groups in total), and intensely monitored for 12-months for a large number of outcomes. Key details of the trial have been recorded at the clinical trial registry at the National Institutes of Health (USA) (www.clinicaltrials.gov), under the registration number NCT00945698. A full trial protocol is available from the contact person to this document.

This document (called "the statistical analysis plan" or SAP) describes the study group's plan for data analysis, management, and storage. The SAP is designed to be evolving over time. Version 1.0 documents the details of the hypothesis testing and other analyses on primary and selected secondary outcomes. Subsequent versions of the SAP will give further details on the analyses and hypothesis testing of additional secondary outcome variables and exploratory analyses from the data.

3 Study objectives

The main aim of the trial is to assess the safety and impact of LNS supplementation on linear growth of infants and young children and to identify individual, household, and village-level characteristics that would modify the effects of LNS on child growth. A secondary aim is to similarly study the impact of LNS on various other (secondary) outcomes in the same target group. Finally, the trial aims to provide descriptive information on issues that might be necessary to facilitate future demand creation for LNS interventions.

The above aims have been broken down into the following first five objectives that were predefined in the trial protocol. The safety aim was not explicitly stated among the predefined objectives in the trial protocol, but was listed under the primary outcomes for analysis.

- 1. To determine the lowest daily dose of LNS that will promote linear growth among 6-18 months old infants in a rural Malawian community with poor food security. *This covers also the objective to study if ANY dose of LNS promotes linear growth among the target group.*

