\sim 12 mo: ASF score (out of 28)		As for ~9.6 m	onth time point		
~12 mo: Lowest ASF tertile (%)	As above	Constructed as above. New variables are asf7T28, and i28_asfT1 through i28_asfT3.	As above		
~12 mo: Fruit/veg score (out of 35)		As for ~9.6 m	onth time point		
~12 mo: Lowest fruit/veg tertile (%)	As above	Constructed as above. New variables are frveg7T28, and i28_frvegT1 through i28_frvegT3.	As above		

Page 14	of 27
---------	--------------

Outcome	Variable name(s)	Location, variable construction	Criteria for errors, outliers	Criteria for transformation	Use of imputation			
~15 mo: Lowest ASF tertile (%)	As above	Constructed as above. New variables are asf7T40, and i40_asfT1 through i40_asfT3.	As above					
~15 mo: Fruit/veg score (out of 35)		As for ~9.6 m	onth time point					
~15 mo: Lowest fruit/veg tertile (%)	As above	Constructed as above. New variables are frveg7T40, and i40_frvegT1 through i40_frvegT3.	As above					
~18 mo: ASF score (out of 28)		As for ~9.6 m	onth time point					
~18 mo: Lowest ASF tertile (%)	As above	Constructed as above. New variables are asf7T52, and i52_asfT1 through i52_asfT3.	As above					
~18 mo: Fruit/veg score (out of 35)	As for ~9.6 month time point							
~18 mo: Lowest fruit/veg tertile (%)	As above	Constructed as above. New variables are frveg7T52, and i52_frvegT1 through i52_frvegT3.	As above					

5. Approach to analysis and exclusions specific to this analysis

All tests will be two-sided, at 5% level of significance.

Since varying numbers of observations are available depending on the time point (i.e., there were a substantial number of missed visits), sample sizes by group will be reported for each time point. If specific outcome variables are missing for more than 10% of infants (with denominator being total records available for the time point) we will report the number of observations used per specific outcome analysis.

First analysis will be by intention-to-treat, but excluding observations that are more than ± 4 weeks (28 days) from the median observed age for visits 0, 16, 28 and 40. That is, at time points, 0, 16, 28 and 40, child age could vary by up to 8 weeks.

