% missing																				
Number completed																				
Total ^c																				

^a Median observed age. Infants were enrolled at 5.5-6.5 months of age. Subsequent data collection time points for infant feeding practices were: 16 weeks, 28 weeks, 40 weeks, and 52 weeks of participation in the study.

^b Group defined by assignment to receive 0 g LNS (control; delayed intervention); 10 g; 20 g; or 40 g.

^c Total number of children who should have been in data set at this time point (excluding permanent loss to follow-up).

LNS 20

All

P-value^b

LNS 40 g (missing) Control LNS^a 10 g Ν g Time of enrollment Baseline sample Endline sample Location of HH (or distances to clinic, market) Baseline sample Endline sample HFIA score at baseline Baseline sample Endline sample HH asset score at baseline Baseline sample Endline sample HH housing quality score at baseline Baseline sample Endline sample HH livestock assets score at baseline Baseline sample Endline sample Number of underfives in the HH at baseline Baseline sample Endline sample Maternal education (in y) Baseline sample Endline sample Child age at baseline (in mo) Baseline sample Endline sample Child sex (% female) Baseline sample Endline sample Child length-for-age z-score (LAZ) at baseline Baseline sample Endline sample

Table 2. Background characteristics of study participants

Child weight-for-length z-score (WLZ) at baseline

Baseline sample

Endline sample

^a LNS=lipid-based nutrient supplement; the quantities indicated are the size of the infant's daily dose, delivered to the household *[indicate weekly or bi-weekly]*.

^b Comparison between intervention groups at each time point; p-value for (describe tests).

Table 3. Feeding practices at enrollment, by intervention group

	\mathbf{N}^{a}	(missing)	Control	LNS ^b 10 g	LNS 20 g	LNS 40 g	All	P-value ^c
Exclusive breastfeeding, infants <6 mo ^d								
Frequency of breastfeeding ^e								
None								
6+ times								
Food groups consumed by the infant yesterday ^f								
Porridge								
Other grain-based foods or roots/tubers								
Any legumes or nuts								
Any dairy (liquids, semi-solids, solids)								
Any meat, poultry or fish								
Any eggs								
Any vitamin A-rich fruit and/or vegetable								
Any other fruit and/or vegetable								
^a Number of infants at enrollment. For exclusive breastfeed	ling n is t	he number of in	fants who w	ere less than 61	monthsofage	at enrollment		

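### Appendix 05, step i: the pooled LNS comparison has an undefined trigger and no alpha of its own; if it follows a non-significant global test, the false-positive risk is about 8.1% per outcome and time point

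*SAP*

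**What the plan says.** Section 5 of Appendix 05 sets the level for the whole appendix: "All tests will be two-sided, at 5% level of significance". The analysis steps are in section 5.4.

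- Step b is the first test: "We will test the null hypothesis of no difference among the four treatment groups (iLiNS-DOSE) using ANCOVA or logistic regression". The footnotes to the Appendix 05 tables define the groups: "Group defined by assignment to receive 0 g LNS (control; delayed intervention); 10 g; 20 g; or 40 g".
- Step c opens further comparisons only after rejection: "if the global null hypothesis is rejected at 0.05 level, then we will perform post-hoc pairwise comparisons of all four groups". These carry multiplicity adjustments, with Scheffé's test for other contrasts.
- Steps f and g add an equivalence assessment for the four quasi-continuous outcomes only (animal-source and fruit/vegetable counts for yesterday, and the two scores for last week).
- Step h says "Confidence intervals will be adjusted for multiple comparisons".
- Step i says, for each outcome, "if results are inconclusive, all LNS groups will be combined and 2-group comparisons will be made, to improve power to detect differences".

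No step defines 'inconclusive' or divides alpha between the test in step b and the test in step i.

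**The concern.** Step i gives a second test on the same data, brought in because the first did not settle the matter, and its stated purpose is to find differences. With no separate level given, the general 5% applies to it. A null outcome then has two chances to be declared different, so the chance of at least one false declaration exceeds the 5% of the global gate.

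Step i also sits badly with step c. Combined LNS versus control is a contrast among the four groups. Step c would let it be examined only after global rejection and at Scheffé's threshold. Step i examines it when the global test has failed, at the ordinary threshold. One comparison therefore has two standards of evidence, depending on the global result.

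The appendix exists because LNS might displace breastfeeding or local foods. A false signal of change bears directly on that question, and a reader of the results could not tell which test carried the conclusion.

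**Working it through.** **Inputs.** Two-sided 5% per test (Appendix 05, section 5). Four groups, so the global test has 3 df and the pooled contrast 1 df. Total size: "a total of 1932 infants were enrolled in rural Malawi" (SAP, Introduction). The split by arm is not given. I assume six equal arms: 1932 / 6 = 322, hence 322/322/644/644 once the milk and milk-free arms are merged by dose. The result hardly depends on this.

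**Step 1, the plan's own figure.** The global test alone gives 5% by construction. Simulation with 322/322/644/644 gives 4.97%.

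**Step 2, both tests, with 'inconclusive' read as a non-significant global test.** In large samples the pooled contrast is one of the 3 df of the global statistic. The critical values are 7.815 (3 df) and 3.841 (1 df). Hence

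P(either rejects) = 0.05 + ∫ from 3.841 to 7.815 of f₁(x) · F₂(7.815 − x) dx,

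where f₁ is the chi-square density on 1 df and F₂ the chi-square distribution function on 2 df. The integral is 0.0314, so the total is **0.0814**. Two independent tests would give 1 − 0.95² = 0.0975, but these two are correlated. Among null outcomes that pass the global test, 0.0314 / 0.95 = 3.3% are then declared different by the pooled test.

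**Step 3, simulation checks of P(either rejects).**

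| Setting | Result |
|---|---|
| Normal outcome, 322/322/644/644 | 8.1% |
| Normal outcome, 240/240/480/480 | 8.1% |
| Normal outcome, four equal groups | 8.2% |
| Binary outcomes, prevalence 10% to 90% | 7.9% to 8.3% |

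The table shells show seven dichotomous outcomes at four follow-up visits. Over 28 null analyses the expected number of false signals is 28 × 0.0814 = 2.3, against 28 × 0.05 = 1.4.

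**Step 4, the narrower reading for quasi-continuous outcomes.** Suppose step i runs only when the result is neither significant nor equivalent. For yesterday's counts, "Margins for yesterday will be ±1.0"; for last week's animal-source score the margin is ±4. The document gives no SDs, so I assume 0.5 to 2.5 for yesterday and 3 to 7 for last week, with groups of 240/240/480/480 and Bonferroni-adjusted intervals over the six pairs. Equivalence is then shown in 93.5% to 100% of null trials, so step i seldom runs. The overall rate stays at about 5%, and reaches 6.1% only at an SD of 2.5 for yesterday's counts.

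**Step 5, step c against step i.** On the large-sample scale, Scheffé's threshold for a 3-df family is 7.815, a nominal P of about 0.005. No contrast can pass it when the global test has failed. Step i applies 3.841 (P = 0.05) in exactly that situation.

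**Step 6, levels that hold 5%.** With 0.025 for each test, the formula in step 2 gives 4.2%. With about 0.030 each, it gives 5.0%.

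**The case against.** The strongest defence is that 'inconclusive' belongs to the equivalence steps it follows. Elsewhere in this SAP the word, or its equivalent, describes an interval that straddles a margin (section 11.4; Appendix 02, 5.2; Appendix 03, section 5; Appendix 08, section 9). On that reading the inflation almost disappears for the quasi-continuous outcomes. This stands for those four outcomes. It cannot serve the dichotomous ones, because step i covers each outcome and they have no margin to straddle. Step i's stated aim of detecting differences also points to non-significance.

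A reader might infer that the SAP promises 5% per outcome and breaks that promise everywhere. It does not: section 5 sets a level per test, each test holds its own level, and no per-outcome error rate is stated.

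A reader might also infer that the contrast is picked after seeing the data. Step i fixes one contrast in advance, the same for every outcome, and gives the reason. The defect is a two-stage procedure without alpha allocation, not selection from a menu. Nor does the text support a second attempt at equivalence after pooling as a firm reading, since step i speaks only of differences.

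Step h is no answer. It concerns confidence intervals and does not link the two tests.

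Finally, these are secondary outcomes for which the trial was not powered, and the hypothesis is that LNS does not change feeding. The extra errors are false alarms. That lowers the stakes but leaves the arithmetic as it is.

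**Conclusion.** The point holds in limited form. The trigger is undefined, and the added test has no alpha of its own. For the dichotomous outcomes the false-positive risk is about 8.1% per outcome and time point, against 5% for the global gate alone. For the four quasi-continuous outcomes it lies between about 5% and 8%, depending on what 'inconclusive' means; an undefined word should not decide that. The 8.1% assumes no true effect, the general 5% level for the pooled test, and large-sample behaviour. It does not depend materially on group sizes or prevalence. It leaves out multiplicity across outcomes and visits. The lower figure for the quasi-continuous outcomes rests on assumed SDs. The conflict between steps c and i stands whenever a failed global test leads to step i.

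**What to change.** Remove the 'if inconclusive' trigger and choose one of two wordings.

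1. Run the combined-LNS versus control contrast for every outcome, with alpha split between it and the global test: 0.025 each (4.2% overall) or about 0.03 each (5.0% overall). State in step c that this contrast has its own allocation and falls outside the Scheffé family.
2. Keep the global test at 5% as the only confirmatory test and label the pooled comparison exploratory.

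Both are changes of wording. The first costs some power: a global test with 80% power at 0.05 has about 71% at 0.025, or about 74% at 0.03. The second costs the global test nothing but gives up any confirmatory claim from the pooled comparison.

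Do not make the dose-specific comparisons conditional on the combined test. With 322/322/644/644, and effects sized so that the global test has 80% power, the combined test at 5% has 18% power if only the 40 g group is affected. It has 59% if the effects at 10, 20 and 40 g stand at 0.25, 0.5 and 1 of the maximum. It gains (91%) only if all doses act alike. Such a gate could hide an effect confined to the highest dose.

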5.5 Covariates in main effects models

In theory, a variety of community-, household-, maternal-, and child-level characteristics could affect child feeding practices independently of the intervention. Data are available for the covariates listed below. All covariates are as measured at baseline, with the exception of child age. Since child age at each visit can vary, child age at time of measure will be included in models. Before making final decisions on inclusion of covariates, completeness of data for the covariates will be considered and covariates will be excluded if loss of sample size is judged too large.

- Month of study during which the child was enrolled
- Characteristics of households
 - o Location of household, or distance to market and distance to clinic

- Baseline HH food security (HFIA score)
- Baseline HH asset score
- o Baseline HH housing quality score
- o Baseline HH livestock assets score
- o Number of underfives in the HH, assessed at baseline
- Maternal education
- Child's characteristics
 - o Child age
 - o Child sex
 - Child length-for-age z-score (LAZ) at baseline
 - o Child weight-for-length z-score (WLZ) at baseline

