1.1 Primary objective

To compare infant and young child feeding practices and summary diet quality variables across intervention groups. Comparisons at baseline are descriptive, to assess comparability of groups. At all later time points, comparisons are to assess the effect of the intervention on IYCF practices.

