1.3 Exploratory analyses

Exploratory analyses will be described later, in separate SAP or in addenda to this SAP. Note that in the sister trial in Burkina Faso ("iLiNS-ZINC"), there is a pre-planned exploratory analysis: description of child feeding practices and factors associated with these practices including food security and seasonality, and relation with nutritional status (growth, iron status, morbidity).

3. Hypotheses to be tested

Stated qualitatively: Provision of LNS would not impact infant and young child feeding practices. More specifically, provision of LNS would not cause a change in:

- Breastfeeding (prevalence of any breastfeeding several time points throughout intervention, and reported frequency of breastfeeding the previous day)
- Frequency of feeding other solids foods (meals and snacks, or feeding episodes)²;

²These data are not yet available and variable construction and analyses are not described in this version.

- Dietary diversity measured as food group diversity at or above the WHO cut-off³;
- Number of nutrient-dense food groups (animal-source foods, fruits and vegetables)

4. Description of infant and young child feeding practice outcome variables

On the following pages, we present information on construction of outcome variables.

The table shows details on: data sources; variable names and variable construction; treatment of data and criteria for imputing missing values.

With few exceptions (detailed in the table) no data will be imputed for analyses of IYCF practices as outcomes.

However, in later analyses where longitudinal IYCF practice variables (e.g. indices summed across time points) may be used as potential effect modifiers, data could be imputed to avoid losing substantial numbers (those for whom data from all time points are not available).

Timing of outcomes: in the iLiNS-DOSE trial, target dates for collection of IYCF practices data were: Baseline (week 0, at ~5.5-6.5 mo of age); week 16; week 28; week 40; and endline (week 52). Data on breastfeeding practices, food group intake, and use of fortified products and vitamin/mineral drops were assessed at all time points. Data on frequency of meals and snacks were collected on KAP questionnaires at 6, 12, and 18 months of age (data not yet available).

³ WHO (2008) Indicators for assessing infant and young child feeding practices: conclusions of a consensus meeting held 6–8 November 2007 in Washington D.C., USA.

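### Appendix 05 records feeding practices at week 0 but does not adjust the feeding outcomes for their own baseline value, so the difference tests give up some efficiency

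*SAP*

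**What the plan says.** Appendix 05, section 4, places feeding data collection at weeks 0, 16, 28, 40 and 52 and adds: "Data on breastfeeding practices, food group intake, and use of fortified products and vitamin/mineral drops were assessed at all time points". The week-0 values have a descriptive role only. Under the primary objective (1.1), "Comparisons at baseline are descriptive, to assess comparability of groups"; under 5.3, "Feeding practices at baseline will be presented, by group" (Table 3).

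The group comparison in 5.4 step b is made "using ANCOVA or logistic regression, and controlling for the prespecified covariates". Step g uses the same covariates for the equivalence models. The list is in 5.5, introduced by "All covariates are as measured at baseline, with the exception of child age". It contains month of enrolment; household location, food security, asset, housing and livestock scores; number of under-fives; maternal education; and child age, sex, LAZ and WLZ. No feeding practice is on it.

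On power, 5.4 says that the study was not sized for the feeding outcomes and that "we are severely underpowered for equivalence analyses, particularly for dichotomous outcomes". It therefore tests for differences first and adds equivalence tests for the quasi-continuous outcomes only.

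**The concern.** In an ANCOVA of a repeatedly measured outcome, the obvious candidate for a prognostic covariate is that outcome's own pre-treatment value. Here it exists and is left out, while less direct predictors such as housing quality and livestock score are kept. The main SAP does otherwise: in 12.6, two of the four models for change in LAZ adjust for baseline LAZ.

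The appendix sets out to show that LNS does not change feeding. A non-significant difference supports that only as far as the test is sensitive. The plan looks for sensitivity elsewhere: step i of 5.4 pools all LNS groups when results are inconclusive. A prognostic measurement already collected should be used before that step. If Table 3 later shows a chance imbalance, adding the covariate then would be a data-driven choice, so it has to be specified beforehand.

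**Working it through.** **Is the omission real?** Section 4 puts the measurement at week 0, 1.1 and 5.3 make it descriptive, and 5.5 does not list it. Nothing else in Appendix 05 adds it to a model.

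**Which outcomes go to which model?** Section 4 defines 11 outcomes at about 9.6 months. Four are quasi-continuous (number of animal-source and of fruit/vegetable groups yesterday, and the two 7-day scores) and suit ANCOVA. Seven are dichotomous (still breastfed, 6+ feeds, 4+ food groups, no animal-source food, no fruit/vegetables, and two lowest-tertile indicators) and go to logistic regression.

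**Inputs.** The SAP states that "a total of 1932 infants were enrolled in rural Malawi"; 1932/6 = 322 per arm if allocation was equal (an assumption). Tests are two-sided at 5%. Appendix 05 gives no SD, no power figure and no baseline-to-follow-up correlation, so there is no stated figure to reproduce, and ρ is varied from 0.1 to 0.5.

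**ANCOVA difference tests.** Residual variance is multiplied by 1 − ρ², the SE by √(1 − ρ²), and effective sample size by 1/(1 − ρ²). For a two-group contrast with 80% power at the start, power = Φ[(1.960 + 0.842)/√(1 − ρ²) − 1.960]. At ρ = 0.3 this is Φ(2.802/0.954 − 1.960) = Φ(0.977) = 83.6%. For the four-group global test, the noncentrality of a 3-df chi-square is divided by (1 − ρ²).

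| ρ | SE factor | Effective n | Two-group power, from 80% | Global test, from 80% | Global test, from 50% |
|---|---|---|---|---|---|
| 0.1 | 0.995 | +1% | 80.4% | 80.4% | 50.4% |
| 0.2 | 0.980 | +4% | 81.6% | 81.8% | 51.8% |
| 0.3 | 0.954 | +10% | 83.6% | 84.0% | 54.2% |
| 0.4 | 0.917 | +19% | 86.4% | 87.0% | 58.0% |
| 0.5 | 0.866 | +33% | 89.9% | 90.8% | 63.4% |

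**Logistic difference tests.** Simulation with 322 per arm, 1500 runs per setting, treatment log odds ratio 0.45, and a binary baseline with prevalence 0.1 to 0.5 and log odds ratio 0.7 to 2.0 (all assumed). Adding the baseline moved the SE of the treatment log odds ratio from 0.159–0.160 up to 0.161–0.180. Power still rose: from 81.1% to 81.2% with the weakest baseline and from 61.7% to 71.8% with the strongest. The gain arises because the conditional log odds ratio moves further from zero than its SE grows.

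**Continued breastfeeding.** Let p0 be the proportion breastfed at week 0 and p1 the proportion later, and suppose no child restarts. The squared correlation is then at most p1(1 − p0)/[p0(1 − p1)]. With assumed p0 of 98% and p1 of 90% this is 0.9 × 0.02/(0.98 × 0.1) = 0.18. With 99.5% and 80% it is 0.8 × 0.005/(0.995 × 0.2) = 0.02.

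**Equivalence tests.** The largest SD that keeps 90% power at a true difference of zero is margin/[(1.645 + 1.645)√(2/n)]. For the ±1.0 margin at n = 322 this is 1/(3.290 × 0.0788) = 3.86, or 3.14 with Bonferroni for six pairs. At n = 206 (an assumed 36% loss) the limits are 3.09 and 2.51. A count from 0 to 5 cannot have an SD above about 2.5. For the 7-day scores at n = 322, the limits are 15.4 for ±4 and 19.3 for ±5 (12.6 and 15.7 with Bonferroni). The largest possible SDs, half the range, are 14 and 17.5. Assumed SDs of 5 to 7 give half-widths of 0.65 to 0.91, or 0.94 to 1.32 with Bonferroni. These tests do not lack precision.

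**The case against.** The strongest reply is that nothing here is wrong: the plan contradicts nothing, the comparison is protected by randomisation, and chance imbalance is already allowed for in the confidence interval. That stands. The omission costs efficiency only.

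The second reply is that ρ may be small. Week 0 falls at about 5.5–6.5 months, and Table 3 reports exclusive breastfeeding in infants under 6 months, so some children may have eaten no food groups at baseline. Several outcomes come from one day's recall, and ρ is partial, given the covariates already in the model. At ρ of 0.1–0.2 the gain is at most about 2 points. That also stands, and the documents cannot settle it.

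Three stronger readings are tempting but not supported.

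- A reader might take "we are severely underpowered for equivalence analyses, particularly for dichotomous outcomes" to mean that the missing covariate weakens the planned equivalence tests. The phrase is about equivalence analyses, chiefly dichotomous ones, and no dichotomous equivalence test is planned. Those that are planned have ample precision at their margins.
- A reader might infer that residual variance is inflated in every difference test. The ρ² reduction belongs to ANCOVA and so to four of the eleven outcomes.
- A reader might suppose that all the week-0 variables are ready in Table 3. That table lacks the 7-day scores, the animal-source and fruit/vegetable counts and the 4+ groups indicator. Section 4 does not separately confirm that the 7-day scores were taken at week 0.

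**Conclusion.** The point holds as an inexpensive improvement in efficiency, not as a source of bias or an error of logic. Appendix 05 leaves a collected, pre-treatment value of each outcome out of difference tests that, by its own statement, the study was not sized for. For the four quasi-continuous outcomes the gain from an 80% start runs from under 1 point (ρ = 0.1) to about 10–11 points (ρ = 0.5). For the dichotomous outcomes the simulated gain was 0.1 to 10 points of power, with no reduction in the SE of the log odds ratio, and it should be small for continued breastfeeding. The equivalence conclusions are unlikely to move. All of this rests on assumed correlations, assumed baseline prevalences and equal allocation.

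**What to change.** Add to the list in Appendix 05, 5.5: *the week-0 value of the same outcome, where collected and where it varies*. Apply it to the models of 5.4 steps b and g. Two further sentences are needed:

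- Children with a missing or excluded week-0 value are kept by mean imputation or a missing indicator. This is acceptable for a pre-randomisation covariate, and without it the rule in 5.5 that drops covariates costing too much sample could remove the new one.
- The covariate is not added to the effect-modifier list in 5.6, which otherwise takes in child-level characteristics and would add an interaction test for each outcome and time point.

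The cost is one degree of freedom per model (two with an indicator) and the construction of the week-0 variables that Table 3 does not hold. The change should be fixed before baseline feeding is examined by group.
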